5. SAMPLE SIZE JUSTIFICATION

No formal statistical assessment, in terms of sample size, has been conducted as this is the first time CPT31 is being administered to humans. However, the number of subjects in the present study is common in early clinical pharmacology studies and is considered sufficient to achieve the objectives of the study. A common distribution between active and placebo subjects is 6+2. Buoen et al. (Evaluation of the Cohort Size in Phase I Dose Escalation Trials Based on Laboratory Data, J Clin Pharmacol (2003) 43:470-476) investigated the impact of cohort size on Type I error and power in Phase I dose escalation trials based on laboratory data and concluded that “the active cohort size in Phase I dose escalation trials should be between 6 and 10 active subjects.”

6. STUDY TREATMENTS

The study treatment names, abbreviations, and ordering to be used in the TFLs are presented in [Table 1](#).

Table 1: Presentation of Study Treatment Sequences in TFLs

Study Treatment Name	Treatment Order on TFLs
Placebo	1
0.01 mg/kg SC CPT31	2

0.04 mg/kg SC CPT31	3
0.12 mg/kg SC CPT31	4
0.24 mg/kg SC CPT31	5

7. DEFINITIONS OF POPULATIONS

Any protocol deviations will be considered prior to database lock for their importance and taken into consideration when assigning subjects to populations.

7.1. All Subjects Population

The all-subjects population will include all subjects who signed the informed consent form and had any study assessment recorded in the database per the protocol.

7.2. Safety Population

The safety population will include all subjects who received at least 1 dose of study treatment (CPT31 or placebo).

7.3. Pharmacokinetic Population

The PK population will include all subjects who received at least 1 dose of CPT31 and have evaluable PK data.

8. STATISTICAL METHODOLOGY

8.1. General

Listings will be provided for all data captured in the database. Listings will include all subjects assigned to the all-subjects population and include data up to the point of study completion or discontinuation. Subjects are generally considered to have completed the study if they completed all protocol-specified procedures and assessments for the end-of-treatment visit. Any subject who discontinued the study will be identified accordingly in the listings. Summaries and statistical analyses will include the subjects assigned to the relevant population based on data type.

Data analysis will be performed using the SAS® statistical software package Version 9.4 (or higher if upversioned during the study).

Analysis Data Model (ADaM) datasets will be prepared using Clinical Data Interchange Standards Consortium (CDISC) ADaM Version 2.1 (or higher if upversioned during the study) and CDISC ADaM Implementation Guide Version 1.2 (or higher if upversioned during the study). Pinnacle 21 Community Validator Version 2.2.0 (or higher if upversioned during the study) will be utilized to ensure compliance with CDISC standards.

Caution should be used when interpreting results from the statistical analyses conducted in this study because the sample size is not based on power calculations.

Where reference is made to 'all calculations', this includes, but is not limited to, summary statistics, statistical analyses, baseline derivation, changes from baseline, percentage changes from baseline, and any parameter derivations.

8.1.1. Calculation of the Summary Statistics

For continuous data the following rules will be applied:

- Missing values will not be imputed, unless specifically stated otherwise.
- Unrounded data will be used in the calculation of summary statistics.
- If the number of subjects with valid observations (n) < 3 , summary statistics will not be calculated, with the exception of n , minimum, and maximum.
- As Early Termination data is not associated with any scheduled timepoint, it will be excluded from all calculations of summary statistics.

For categorical data the following rules will be applied:

- If the categories of a parameter are ordered (eg, AE severity), all categories between the possible minimum and maximum categories will be included, even if $n = 0$ for a given category. If the categories are not ordered (eg, race), only those categories for which there is at least 1 subject represented will be included.
- Missing values will not be imputed, with the exception of AEs where the 'worst-case' approach will be taken (see [Section 8.6.1](#)), or unless specifically stated otherwise. A 'missing' category will be included for any parameter for which information is missing. This will ensure that the population size totals are consistent across different parameters.

8.1.2. Triplicate Readings

For vital signs data only, where triplicate readings are taken, the median of triplicate readings will replace the original readings in all calculations.

For electrocardiogram (ECG) data only, where triplicate readings are taken, the mean of triplicate readings will replace the original readings in all calculations.

In case of incomplete triplicate readings (eg, only 2 out of 3 readings were recorded), the mean and/or medians will be calculated based on the number of readings available.

8.1.3. Repeat and Unscheduled Readings

For vital signs and ECG data only, any predose value recorded in addition to the original value or a postdose value recorded within 15 minutes of the original value will be defined as a repeat value; any postdose value recorded more than 15 minutes after the original value will

be defined as an unscheduled value. For all other data types (eg, laboratory parameters), any value recorded in addition to the original value will be defined as an unscheduled value.

The original value will be replaced by the last associated repeat value in all calculations.

As unscheduled values are not associated with any scheduled timepoint, they will be excluded from all calculations, with the exception of the baseline derivation (see Section 8.1.4).

8.1.4. Definitions of Baseline and Change from Baseline

The baseline will be defined as the last value recorded prior to dosing. If the date/time of the value is incomplete or missing, it will be excluded from the baseline calculation, unless the incomplete date/time indicates the value was recorded prior to dosing.

Individual changes from baseline will be calculated by subtracting the individual subject's baseline value from the value at the timepoint. The mean change from baseline will be defined as the mean of the individual changes from baseline for all subjects.

See [Section 8.1.3](#) for more detail on handling repeat and unscheduled readings in the calculations. See [Section 8.1.2](#) for more detail on handling of triplicate readings in the calculations.

8.2. Subject Disposition and Population Assignment

Subject disposition and population assignment will be listed.

A summary table by treatment will be provided, based on the all-subjects population.

8.3. Screening Demographics

The screening demographics including age, sex, race, ethnicity, height, body weight, and body mass index will be listed.

A summary table by treatment will be provided, based on the safety population.

8.4. Prior and Concomitant Medication

Prior medication will be defined as medication that ends prior to dosing. Concomitant medication will be defined as medication that starts during or after dosing or starts but does not end prior to dosing.

Prior and concomitant medications will be coded using the World Health Organization Drug Dictionary (WHODrug) Global, Format B3, Version March 2020 (or later if upversioned during the study). Prior and concomitant medications will be listed.

8.5. Pharmacokinetic Assessments

8.5.1. Pharmacokinetic Analysis

The following PK parameters will be determined where possible from the plasma concentrations of CPT31, using non-compartmental methods in validated software program, Phoenix WinNonlin (Certara USA, Inc., Version 8.1 or higher):

Parameter	Units	Definition
AUC _{0-t_{last}}	h*xg/mL	area under the curve from time 0 to the time of the last measurable concentration ^a
AUC _{0-∞}	h*xg/mL	area under the curve from time 0 to infinity ^b
C _{max}	xg/mL	maximum concentration
T _{max}	h	time to maximum concentration
T _{last}	h	time of the last quantifiable plasma concentration
t _{1/2}	h	apparent terminal elimination half-life
CL/F	L/h	apparent total plasma clearance
V _{z/F}	L	Apparent volume of distribution during the terminal elimination phase
%AUC _{extrap}	%	percentage of AUC due to extrapolation from the last quantifiable concentration to infinity
A _e	mg	amount of drug excreted in the urine at each collection interval and cumulative amount of drug excreted in the urine at each collection interval
F _e	%	percentage excreted in urine at each collection interval and cumulative percentage excreted in urine at each collection interval
CLR	h*xg/mL/mg	renal clearance

a AUC will be calculated using the linear trapezoidal rule for increasing concentrations and the logarithmic rule for decreasing concentrations (linear up/log down rule). Additional pharmacokinetic parameters may be determined where appropriate.

b Based on last observed quantifiable concentration

Additional PK parameters may be determined where appropriate.

Actual elapsed time from dosing will be used to estimate all individual PK parameters. If actual times are missing, nominal times may be used by default.

If AUC_{0-∞} cannot be determined for all subjects, an alternative AUC measure, such as AUC to a fixed time point, may be used in the statistical analysis.

C_{max}, T_{max} and T_{last} will be obtained directly from the concentration-time profiles. For multiple peaks, the highest postdose concentration will be reported as C_{max}. In the case that multiple peaks are of equal magnitude, the earliest T_{max} will be reported.

The amount of drug excreted in urine (A_e) and percentage of dose excreted (F_e) will be calculated for each urine collection (t₁-t₂); cumulative A_e and F_e will be calculated by

summing the t_1-t_2 values over the 0- t_2 period where t_2 = end of the study collection period. A_e will be calculated using a urine density of 1.0 g/mL.

CL_R will be calculated over the same collection interval according to the following formula, at the time interval (0- t_2) where concentrations are quantifiable for both parameters:

$$CL_R = \frac{Ae_{0-t_2}}{AUC_{0-t_2}}$$

8.5.1.1. Criteria for Handling Concentrations Below the Limit of Quantification or Missing Concentrations in Pharmacokinetic Analysis

For the non-compartmental analysis (NCA) and individual plot, if a BLQ value occurs before the first measurable concentration, it will be assigned a value of 0, otherwise it will be treated as missing. The following rules apply with special situations defined below:

- Where 2 or more consecutive concentrations are BLQ at the end of a profile, the profile will be deemed to have terminated and any further quantifiable concentrations will be set to missing for the calculation of the PK parameters unless they are considered to be a true characteristic of the profile of the drug.
- If an entire concentration-time profile is BLQ, the profile will be excluded from the PK analysis.
- If a pre-dose measurement for the first dose is missing, the value will be set to zero.

8.5.1.2. Criteria for Calculating an Apparent Terminal Elimination Half-life

The start of the terminal elimination phase for each subject will be defined by visual inspection and will be the first point at which there is no systematic deviation from the log-linear decline in plasma concentrations.

The apparent terminal elimination rate constant (λ_z) will only be calculated when a reliable estimate can be obtained using at least 3 data points, preferably not including C_{max} , and the adjusted coefficient for determination of exponential fit (R^2 -adj) of the regression line is ≥ 0.7 . Parameters requiring λ_z in their calculation (eg, AUC_{0-inf} , $t_{1/2}$, CL/F and V_z/F) will only be calculated if the R^2 -adj value of the regression line is ≥ 0.7 .

The following regression-related diagnostic PK parameters will be determined:

Parameter	Units	Definition
λ_z	h^{-1}	apparent terminal elimination rate constant
λ_z Upper	h	end of exponential fit
λ_z Lower	h	start of exponential fit
λ_z N	NA	number of data points included in the log-linear regression
λ_z Span Ratio	NA	time period over which λ_z was determined as a ratio of $t_{1/2}$
R^2 -adj	NA	adjusted coefficient for determination of exponential fit

The time period used for the estimation of apparent terminal elimination half-lives, where possible, will be over at least two half-lives. For $t_{1/2}$ estimates where λ_z was calculated over a time period less than twice their resultant half-life, the reliability of $t_{1/2}$ and any PK parameters derived from λ_z will be discussed in CSR.

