### **3.1. Overall Study Design and Plan**

This study will comprise a placebo-controlled, double-blind, single-dose, sequential-group design. Overall, it is planned for 32 healthy subjects to be studied in 4 groups (Groups A1 to A4), with each group consisting of 8 subjects. In each group, 6 subjects will be randomized to receive SC CPT31 and 2 subjects will be randomized to receive matching placebo.

Potential subjects will be screened to assess their eligibility to enter the study within 28 days prior to the first dose administration.

Each subject will participate in 1 treatment period only. Subjects will reside at the Clinical Research Unit (CRU) from Day -1 (the day before dosing) to Day 6. All subjects will return for a Follow-up visit 28 to 30 days after dosing.

Based on the ongoing review of the safety, tolerability, and PK results, additional nonresidential visits may be required. The number of additional visits per subject will not exceed 3 and will not extend beyond 30 days after dose administration.

[figure not shown]
All groups will be divided into 2 cohorts, with each cohort being dosed 72 hours apart. The first (sentinel) cohort will comprise 2 subjects, with 1 subject receiving CPT31 and 1 subject receiving placebo. The second cohort will comprise 6 subjects, with 5 subjects receiving CPT31 and 1 subject receiving placebo.

The maximum total duration of study participation for each subject (from Screening through Follow-up visit) is anticipated to be approximately 8 weeks.

Dose escalation will occur a minimum of 7 days after all subjects complete all Day 6 assessments in the previous dose group.

[figure not shown]
An overview of the study design is shown in [Figure 1](#) and the planned dose levels in are shown in [Figure 2](#). A Schedule of Assessments is presented in [Appendix 6](#).

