### 7.1. Pharmacokinetic Assessments

#### 7.1.1. Sample Collection and Processing

Blood samples (approximately  $2 \times 1$  mL) will be collected by venipuncture or cannulation at the times indicated in the Schedule of Assessments in [Appendix 6](#). Furthermore, up to 3 additional blood samples may be taken from each subject, with the maximum volume of blood withdrawn per subject not exceeding the limit detailed in [Appendix 3](#). Any changes to the scheduled times of PK assessments will be agreed with the Sponsor and documented in the TMF. Samples taken from subjects who received placebo will not be analyzed.

Procedures for collection, processing, and shipping of PK blood samples will be detailed in a separate document.

Urine samples, for male subjects only, will be collected into pre-weighed polyethylene containers over the time intervals indicated in the Schedule of Assessments in [Appendix 6](#). Procedures for collection, processing, and shipping of urine samples will be detailed in a separate document.

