8.6.3. Vital Signs Parameters

All vital signs parameters, with changes from baseline will be listed; any value outside the clinical reference range will be flagged.

Summary tables and boxplots by treatment and timepoint will be provided for all vital signs parameters, with changes from baseline.

8.6.4. 12-lead Electrocardiogram Parameters

All 12-lead ECG parameters, with changes from baseline, will be listed; any value outside the clinical reference range will be flagged.

Summary tables and boxplots by treatment and timepoint will be provided for all 12-lead ECG parameters, with changes from baseline. An outlier analysis will be performed for QT interval corrected for heart rate using Bazett's formula (QTcB) and QT interval corrected for heart rate using Fridericia's formula (QTcF). The analysis will include all individual original, repeat, and unscheduled postdose values.

The maximum postdose values will be summarized by treatment according to the following categories:

- ≤ 450 ms
- >450 and ≤ 480 ms (all instances flagged in the listing)
- >480 and ≤ 500 ms (all instances flagged in the listing)
- >500 ms (all instances flagged in the listing)

The maximum increases from baseline will be summarized by treatment according to the following categories:

- ≤ 30 ms
- >30 and ≤ 60 ms (all instances flagged in the listing)
- >60 ms (all instances flagged in the listing)

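### Read literally, the SAP's rule on unscheduled values keeps the protocol's additional PK samples out of the noncompartmental analysis, and no PK exemption resolves the conflict with the PK section

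*SAP*

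**What the plan says.** **Additional samples.** Protocol 7.1.1 says that "up to 3 additional blood samples may be taken from each subject". Protocol 3.1 says that, depending partly on the PK results, "additional nonresidential visits may be required", at most 3 per subject and within 30 days of dosing. In the Appendix 6 schedule the last PK sample is at 120 h.

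**General SAP rule.** For data other than vital signs and ECG, SAP 8.1.3 says "any value recorded in addition to the original value will be defined as an unscheduled value". It continues: "As unscheduled values are not associated with any scheduled timepoint, they will be excluded from all calculations, with the exception of the baseline derivation". SAP 8.1 says what counts as a calculation, and its list ends with "percentage changes from baseline, and any parameter derivations".

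**PK section.** SAP 8.5.1 derives the parameters from the plasma concentrations at actual elapsed time. SAP 8.5.1.4, on anomalous values, asks for strong justification and CSR documentation when data are excluded. SAP 8.5.2.1 removes samples taken more than 10% off nominal time from the concentration summaries. On the span of the terminal fit, SAP 8.5.1.2 says: "The time period used for the estimation of apparent terminal elimination half-lives, where possible, will be over at least two half-lives". If the span is shorter, reliability is discussed in the CSR.

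**The concern.** Lambda-z, half-life, AUC to infinity, CL/F and Vz/F are all derived parameters, so the general rule reaches them. Where the SAP wants unscheduled values used, it says so. Baseline derivation is one case. The QTc outlier analysis in SAP 8.6.4 is another: "The analysis will include all individual original, repeat, and unscheduled postdose values". Sections 8.5.1 to 8.5.3 contain no matching statement for PK.

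If samples are drawn after 120 h, the general rule says to leave them out of the NCA and the PK section suggests using them. With nothing to settle this, the choice could be made after concentrations are known, and differently across subjects. The parameters at stake are secondary endpoints, and AUC to infinity also enters the dose-proportionality model in SAP 8.5.3.

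**Working it through.** **1. Are the additional samples planned for?** Appendix 6 lists 15 PK times: predose, 0.5, 1, 2, 4, 6, 8, 10, 12, 16, 24, 48, 72, 96 and 120 h. Adding 3 gives 18, and 18 x 2 mL = 36 mL. Appendix 3 gives 18 samples and 36 mL, and its total also reproduces: 100 + 3.5 + 21.6 + 36 + 8 = 169.1 mL. The extras are therefore in the blood budget.

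**2. When do the scheduled samples meet the two-half-life aim?** The longest half-life that meets it is (120 - start of fit)/2:

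| Fit starts at | Longest half-life |
|---|---|
| 12 h | 54 h |
| 24 h | 48 h |
| 48 h | 36 h |
| 72 h (last three points) | 24 h |

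**3. What half-life might apply?** The documents give no human value. Protocol 3.5 projects, for 0.03 mg/kg every third day, Cmax of about 452 ng/mL and troughs of 117 to 199 ng/mL. I assume mono-exponential decline over 72 h from that Cmax to each trough:

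- 72 x ln 2 / ln(452/117) = 36.9 h
- 72 x ln 2 / ln(452/199) = 60.8 h

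As a cross-check, suppose 13 nM is the first trough and 22 nM the steady-state trough. Then exp(-72k) = 1 - 13/22 = 0.409, which gives a half-life of 55.8 h, inside that range. The monkey SC half-life in Protocol 1.5 is 18.6 h.

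**4. Span of the scheduled fit, in half-lives.**

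| Half-life | 24 to 120 h | 48 to 120 h | 24 to 168 h |
|---|---|---|---|
| 36.9 h | 96/36.9 = 2.60 | 72/36.9 = 1.95 | 144/36.9 = 3.90 |
| 60.8 h | 96/60.8 = 1.58 | 72/60.8 = 1.18 | 144/60.8 = 2.37 |
| 18.6 h | 96/18.6 = 5.16 | 72/18.6 = 3.87 | 144/18.6 = 7.74 |

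**5. Precision of lambda-z.** For a log-linear fit with constant residual SD, SE = SD / sqrt(Sxx), where Sxx is the sum of squared deviations of the sampling times from their mean. The 168 h time is illustrative.

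- Fit from 24 h: Sxx = 5760 without and 13440 with 168 h. The SE ratio is sqrt(5760/13440) = 0.65, a 35% reduction.
- Fit from 48 h: Sxx = 2880 without and 8525 with 168 h. The SE ratio is sqrt(2880/8525) = 0.58, a 42% reduction.

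The formula depends only on the times, so the percentage holds for any half-life if the sample is quantifiable. At 18.6 h, however, 168 h is 9.0 half-lives after dosing and the scheduled span is already 5.16, so little is gained.

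**The case against.** A reader might infer that the SAP definitely bars these samples, that they are the only way to follow the profile beyond 120 h, and that the draws would be wasted. The documents do not support this.

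- The definition in SAP 8.1.3 covers a value recorded on top of an existing one, with laboratory parameters as the example. A draw at a new time has no existing value to add to. The stated reason, that the value belongs to no scheduled timepoint, does describe such a draw. So the rule fits imperfectly but cannot be set aside.
- The PK section leans towards use. It works from the concentration profile at actual times, has its own exclusion rules, and does not list additional samples among them. This stands, with limits: actual elapsed time settles which clock applies rather than which samples enter, and the strong-justification sentence was written for anomalous values.
- Protocol 7.1.1 also lets scheduled PK times be changed with sponsor agreement and a TMF record. A late time adopted that way could count as scheduled.
- Nothing says that the 3 extras are late samples or meant for lambda-z.
- The two-half-life aim applies where possible, and missing it leads only to CSR discussion. Under the assumption in step 3, the AUC share beyond 120 h is 2^(-120/36.9) to 2^(-120/60.8), or about 11% to 25%. That is below the 30% at which SAP 8.5.1.3 allows AUC to infinity to be left out.
- The LLOQ is not given, so a late sample may be below it, most plausibly at 0.01 mg/kg.

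These points limit the size and certainty of the problem. None supplies the missing rule.

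**Conclusion.** The point holds as an unresolved conflict between the SAP's general and PK-specific rules, not as a definite bar. Applied literally, SAP 8.1.3 with 8.1 would drop valid concentrations from the NCA, and no PK exemption prevents it.

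It matters only if additional samples are taken after 120 h, are quantifiable, and the human half-life is long. At the implied 37 to 61 h, a fit from 24 h spans about 1.6 to 2.6 half-lives, so the scheduled samples meet the aim at the short end and miss it at the long end. One 168 h sample would then reduce the standard error of lambda-z by about 35%, or 42% with a 48 h start. At 18.6 h the gain is small.

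These figures rest on mono-exponential decline, on the projected Cmax and trough belonging to the same dosing interval, on the chosen start of the terminal phase, and on constant residual error on the log scale. No primary endpoint is affected. This is a clarification worth making before database lock.

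**What to change.** In SAP 8.1.3, state that the exclusion of unscheduled values does not apply to PK concentrations. All PK samples, scheduled or additional, enter the NCA at actual elapsed time, and additional samples are omitted only from concentration summaries by nominal time. Cross-refer to this in SAP 8.5.1. The treatment matches SAP 8.5.2.1, which already removes off-time samples from the summaries only. The existing rules on BLQ and anomalous values continue to apply.

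The cost is one added statement and a cross-reference. No new data, samples or subjects are needed.
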